2.3.3 Unexpected Adverse Event

An AE is “unexpected” when its nature (specificity) or severity is not consistent with applicable product information, such as safety information provided in the Investigators’ Brochure (IB), the investigational plan or the protocol.

2.3.4 Definitions and Derivations

The following definitions and derivations will be used in this study:

- Diarrhea is defined as ≥ 3 looser than normal stools in a 24 hour period.
- A baseline value will be defined as the last value obtained prior to the first vaccination of study product.
- Age will be calculated from the date of enrollment and will be presented in whole years for adults, months for toddlers and days for infants (truncated integer).
- The calculations for GMTs will be performed by taking the anti-log of the arithmetic mean of the \log_{10} -transformed titers.
- Fold increase/rise from baseline will be calculated as the following:

$$\text{Ratio of: } \frac{\text{post-immunization titer}}{\text{pre-immunization titer}}$$

- Calculation of geometric mean fold rise (GMFR) will be performed by taking the anti-log of the arithmetic mean of the difference in \log_{10} titers, where

$$\text{Difference} = (\text{post-immunization } \log_{10} \text{titer}) - (\text{pre-immunization } \log_{10} \text{titer})$$

- Antibody responses are defined as:
 - **Anti-P2-VP8 IgG & IgA seroresponses by ELISA:** 4-fold increase from baseline in antibody titers in assays using each of the three vaccine antigens (P[4], P[6] and P[8]).
 - **Neutralizing antibody responses:** 2.7-fold increase from baseline in antibody titers to each of the three rotavirus strains from which the vaccine antigens are derived, as well as heterologous strains.
- Prior medications are those medications that started and stopped prior to study vaccination.

3 INVESTIGATIONAL PLAN

3.1 Overall Study Design and Plan

The trial is a double-blind, randomized, placebo-controlled dose-escalation study in which two dose-levels (30 µg and 90 µg) of vaccine will be tested in adults and toddlers and then three dose-levels will be assessed in infants (15 µg, 30 µg and 90 µg).

In **Group A**, cohorts of 15 adults (12 vaccine and 3 placebo recipients) per dose level will receive three study injections at 4 week intervals (consistent with the regimen in the adult study of the monovalent vaccine), advancing from the first to the second dose-level after assessment of safety data through the first week after the first injection (A1).

Based on the safety data in the adult group, **Group B** cohorts of 15 toddlers (12 vaccine recipients and 3 placebo recipients) per dose level will receive a single intramuscular injection (consistent with the regimen administered to toddlers in the current study of the monovalent vaccine in toddlers), advancing from the first to the second dose-level after assessment of safety data through the first week after the injection in the lower dose toddler group (B1) and all available data for the adult group.

Based on the safety data in group B toddler cohorts, **Group C** cohorts of 16 infants (12 vaccine recipients and 4 placebo recipients) per dose level will receive three study injections at 4 week intervals (concomitant with EPI vaccinations, with the exception of rotavirus vaccination), starting at ≥ 6 and < 8 weeks of age. Advancing from the first to the second dose-level in Group C will occur after assessment of safety data through the first week after the first injection (C1), as well as all available data for toddlers and adults. Advancing from the second to the third dose-level (90 µg) in Group C will occur after assessment of safety data through the first week after the first injection of the second dose-level (30 µg).

If all three dose levels are tolerated in the group C infant dose-escalation phase they will be assessed in an expanded infant cohort (**Group D**) of 552 infants (138 at each dose level and 138 placebo recipients). All infants will receive Rotarix at 4, 8 and 12 weeks after the third study injection (study Days 84, 112 and 140), and **fecal shedding** of Rotarix will be assessed during the week after the first dose in a subset of infants. Three doses of Rotarix are to be administered rather than two to counterbalance the remote theoretical possibility that the P2-VP8 subunit vaccine could reduce response to Rotarix.

3.2 STUDY SCHEMA

Group		Trivalent P2-VP8 Dose	N	-7 ^a to -1	0	7	28	56	84	89, 91, 93	168	224
A Adult	A1	30 µg	12	B(S,I)	X	B(S)	X, B(I)	X, B(I)	B(I)			F
		Placebo	3	B(S,I)	P	B(S)	P, B(I)	P, B(I)	B(I)			F
	A2	90 µg	12	B(S,I)	X	B(S)	X, B(I)	X, B(I)	B(I)			F
		Placebo	3	B(S,I)	P	B(S)	P, B(I)	P, B(I)	B(I)			F
A Total			30									
B Toddler	B1	30 µg	12	B(S,I)	X	B(S)	B(I)				F	
		Placebo	3	B(S,I)	P	B(S)	B(I)				F	
	B2	90 µg	12	B(S,I)	X	B(S)	B(I)				F	
		Placebo	3	B(S,I)	P	B(S)	B(I)				F	
B Total			30									
C Infant	C1	15 µg	12	B(S,I)	X	B(S)	X	X, B(I)	B(I)	Sh		F
		Placebo	4	B(S,I)	P	B(S)	P	P, B(I)	B(I)	Sh		F
	C2	30 µg	12	B(S,I)	X	B(S)	X	X, B(I)	B(I)	Sh		F
		Placebo	4	B(S,I)	P	B(S)	P	P, B(I)	B(I)	Sh		F
	C3	90 µg	12	B(S,I)	X	B(S)	X	X, B(I)	B(I)	Sh		F
		Placebo	4	B(S,I)	P	B(S)	P	P, B(I)	B(I)	Sh		F
C Total			48									
D Infant		15 µg	138	B(S,I)	X		X	X, B(I)	B(I)	Sh		F
		30 µg	138	B(S,I)	X		X	X, B(I)	B(I)	Sh		F
		90 µg	138	B(S,I)	X		X	X, B(I)	B(I)	Sh		F
		Placebo	138	B(S,I)	P		P	P, B(I)	B(I)	Sh		F
D Total			552									
All Cohorts Total			660									

X = Trivalent P2-VP8 vaccine

P = placebo

B = blood sample for (S) safety and/or (I) immunogenicity testing

F = final study f/u visit/call

Sh = stool samples to assess Rotarix shedding. Only at RMPRU (Soweto).

^aFor adult and toddler cohorts, -28 to -1

For each age group, progression from one dose level to the next will require review of clinical and safety lab data through 7 days after the first dose at the lower dose level. Safety laboratory blood specimens will be drawn at baseline for all participants (screening) and 7 days after first study injection in Groups A, B and C.

[figure not shown]
Blood samples for immunogenicity analysis will be obtained at baseline for all participants, Days 28, 56 and 84 for Group A (adults), Day 28 for Group B (toddlers), and Days 56 and 84 for Groups C and D (infants).

Stool samples to assess Rotarix shedding will be obtained from infants (Groups C and D) on days 89, 91 and 93 (i.e., 5, 7 and 9 days after the first Rotarix dose on day 84) in the subset of infants enrolled at the Respiratory and Meningeal Pathogens Research Unit (RMPRU).

For each dose level, progression from adults in Group A to toddlers in Group B and then to infants in Group C will require review of clinical and safety laboratory data through 7 days after study injection in the older group. (see Figure 1)

These determinations will be made by the Safety Review Committee (SRC).

Figure 1: Study overview and timeline

Note:

Time line does not take into account delay of enrollment of infant groups until after peak of rotavirus season.

3.3 Selection of Study Population

This study is a multi-site clinical trial, to be performed in South Africa at the Family Clinical Research Unit (FAM-CRU) at Tygerberg Children's Hospital, the Respiratory and Meningeal Pathogens Research Unit (RMPRU) in Soweto, and the Shandukani Research Centre in Hillbrow, Johannesburg. The study population will be recruited, screened and qualified by site staff under the direction of the PIs at each site. Adult and toddler participants will be enrolled only at RMPRU.

Participants are in general good health: in the adult group, participants will be ≥ 18 and ≤ 45 years of age; in the toddler cohort, participants will be ≥ 2 and < 3 years of age; and the infant cohorts will be ≥ 6 and < 8 weeks old at the time of enrollment. Potential volunteer families of infants may be contacted from before the babies were born through the noted targeted age. Final eligibility determination depended on the results of the medical history, clinical examination, screening laboratory tests, fulfillment of all the inclusion criteria, absence of any of the exclusion criteria, appropriate understanding of the study and completion of the consent process by adult participants and parents of toddler and infant participants.

Investigators use good clinical judgment in considering a participant's overall fitness for inclusion in the trial. Some participants may not be appropriate for the study even though they met all inclusion/exclusion criteria. For instance, medical, occupational or other conditions present in the parents may have made safety evaluations difficult or made toddlers and infants poor candidates for retention. The parents of all toddlers and infants targeted for enrollment have to comprehend the purpose of the study and provide written informed consent. In addition, the adult participants and families of toddler and infant participants should be resident in the area without plans to leave the study site during the course of the study.

A sufficient number of healthy adults, toddlers and infants are to be screened, with consent, to enroll 30 adults, 30 toddlers and 600 infants in the study.

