5.4 Covariates and Subgroups

There is no *a priori* plan to summarize the immunogenicity or safety endpoints for covariates. The protocol is set up as a descending age-group study, so each age-group will be summarized separately. The 3 age groups to be analyzed are adults (18-45 years), toddlers (2 to <3 years) and infants (6 to <8 weeks). Safety endpoints for infants will be presented for each site and for all sites combined.

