5.7 Multicenter Studies

This study is being conducted at 3 sites: the Respiratory and Meningeal Pathogens Research Unit (RMPRU) in Soweto enrolled all participants in groups A to C. Group D infants were enrolled at 3 sites: RMPRU, SRC (Shandukani Research Centre) and FAM-CRU (Family Clinical Research Unit, Tygerberg). All summary tables, graphs and listings for infants in groups C and D will be reported by site and for all 3 sites combined.

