7 STATISTICAL ANALYSIS

Descriptive statistics (mean, standard deviation, median, range) for continuous measures (e.g., age) and proportions for categorical measures (e.g., gender) will be summarized by treatment group. All percentages will be presented to one decimal place. Means, medians, standard deviations, confidence intervals, etc., will be presented as integers if the absolute value is greater than or equal to 100 in magnitude, to one decimal place if greater than or equal to 10, and 2 decimal places if less than 10. P-values will be reported to 4 decimal places.

For both safety and immunogenicity, when the use of descriptive statistics to assess group characteristics or differences is required, the following methods will be used: for categorical variables/responses, the number, proportion (% and exact 95% confidence interval) of participants in each category. For continuous variables/responses, the mean, median, standard deviation, quartiles and range, as well as the geometric mean and 95% confidence interval for immunogenicity outcomes. A non-parametric method (e.g., bootstrap or Wilcoxon rank sum test) will be used for continuous variables if the data are not consistent with the normal distribution.

The following methods will be used for formal testing of differences between study groups: for binomial response variables logistic regression will be used to test for an overall treatment effect and, if statistically significant, p-values from all pair-wise comparisons obtained from the regression model will be reported. Where multiple results are available for the same participant (e.g., reactogenicity after each vaccination), the correlation between results from the same participant will be taken into account by using a generalized mixed effects model, with treatment group as a fixed effect and participant as a random effect. For continuous variables that are not normally distributed, the overall treatment effect will be assessed by the Kruskal-Wallis test and if statistically significant, pair-wise comparisons will be performed using the Wilcoxon 2-sample test. For \log_{10} immunogenicity values the overall treatment effect will be assessed by ANOVA and if statistically significant, estimates of all pair-wise comparisons from the model will be reported.

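### Group D comes from three sites, but the pooled infant tests fit treatment alone: valid tests that give up some power if sites differ

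*SAP*

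**What the plan says.** **Sites.** SAP section 3.3 describes the trial with "This study is a multi-site clinical trial, to be performed in South Africa" and names three centres. Section 5.7 has RMPRU enrolling all of Groups A to C, while Group D is spread over all three. Group D is 552 infants and Group C is 48 (section 3.2).

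**Reporting.** Section 5.7: "All summary tables, graphs and listings for infants in groups C and D will be reported by site and for all 3 sites combined". Section 5.4: "Safety endpoints for infants will be presented for each site and for all sites combined". Section 5.4 also disclaims any advance "plan to summarize the immunogenicity or safety endpoints for covariates".

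**Tests.** Section 7 fixes the models:
- Binary endpoints: "for binomial response variables logistic regression will be used to test for an overall treatment effect".
- Repeated binary results, such as reactogenicity after each injection: a mixed model "with treatment group as a fixed effect and participant as a random effect".
- Log10 titers: "immunogenicity values the overall treatment effect will be assessed by ANOVA", with Kruskal-Wallis and Wilcoxon tests where normality fails.

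Sections 7.1.4 and 7.1.5 repeat the same treatment-group tests endpoint by endpoint. The SAP nowhere puts site in a model or uses a site-stratified test. Section 3.3.4 gives Group D a 1:1:1:1 allocation and does not mention site.

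**The concern.** By-site tables do not take site variation out of a test that pools the sites. Site is recorded for every infant and is a natural source of variation here. Reactions are collected by interview and memory aid and assessed at the site (section 3.4.1.1), and the site assigns AE severity grades (section 3.4.1.2). Four of the five safety endpoints in section 4.1.1, the only ones given p-values (section 7.1.1), turn on a moderate-or-greater threshold. Baseline titers may also differ between catchments.

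What is at stake is efficiency. In the ANOVA, site variation stays in the residual. In logistic regression, leaving out a prognostic factor pulls the odds ratio towards 1. The overall test also gates the pairwise comparisons (sections 5.8 and 7), so a less sensitive overall test can stop a dose or safety contrast from being examined. There is least slack in the 15-point seroresponse contrast, planned at 74% power (section 4).

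**Working it through.** **Inputs from the SAP.** Log10 SD 0.6; 135 evaluable infants per group; a 2-fold GMT ratio, so a difference of 0.301; 65% vs 80% and 60% vs 80% seroresponse; two-sided 5% (sections 4 and 7). Group D has 138 per arm.

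**Inputs assumed.** The SAP gives no between-site variance or site-specific rates, so each is taken over a range, with three equal sites. Power below is for two-arm contrasts, not for the overall four-arm test.

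**Step 1. Reproduce the plan.** SE = 0.6 × √(2/135) = 0.0730, and 0.301/0.0730 = 4.12. Power ≈ Φ(4.12 − 1.96) = 98.5% by the normal approximation and 98.4% by the noncentral t, against 98% stated. Fisher's exact test by enumeration gives 75.3% for 65% vs 80% (stated 74%) and 93.9% for 60% vs 80% (stated 95%; the normal approximation gives 95.2%). The planning figures are reproduced to within about a point.

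**Step 2. GMT contrast with site in the model.** Let f be the share of log10-titer variance lying between sites. If the SD of 0.6 includes site variation, adjusting leaves a residual SD of 0.6 × √(1 − f). For f = 10% that is 0.569.

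| f | 2-fold, unadjusted | 2-fold, site in model | 1.5-fold (illustrative), unadjusted | 1.5-fold, site in model |
|---|---|---|---|---|
| 1% | 98.4% | 98.5% | 67.1% | 67.7% |
| 5% | 98.4% | 98.8% | 67.1% | 69.5% |
| 10% | 98.4% | 99.1% | 67.1% | 71.8% |
| 20% | 98.4% | 99.6% | 67.1% | 76.8% |

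The 2-fold gain is 0.1 to 1.2 points. If 0.6 is instead the within-site SD, the unadjusted test has SD 0.6/√(1 − f) and its power falls from 98.4% to 98.3%, 98.0%, 97.4% and 95.7% at the same values of f.

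**Step 3. Seroresponse, 65% vs 80%.** Likelihood-ratio logistic tests, 6,000 simulated trials per row, 45 per arm per site, overall rates held at 65% and 80%. These run higher than the Fisher figure in Step 1 because Fisher's test is conservative.

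| Site logit offsets | Treatment only | Treatment + site |
|---|---|---|
| ±0.25 | 80.2% | 80.6% |
| ±0.5 | 79.8% | 81.0% |
| ±0.75 | 80.6% | 82.8% |
| ±1.0 | 81.4% | 84.5% |

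The gain is about 0.5 to 3 points.

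**Step 4. Event rates.** Pooled chi-square against the Cochran-Mantel-Haenszel test stratified by site, 46 per arm per site (3 × 46 = 138), odds ratio 2.0 (for the three modest spreads, log odds ratio 0.70, or 2.01).

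| Placebo rates at the three sites | Pooled | Stratified |
|---|---|---|
| 30/30/30% | 79.8% | 79.6% |
| 5/10/15% | 48.6% | 49.5% |
| 10/15/20% | 62.0% | 62.8% |
| 15/20/25% | 71.1% | 71.6% |
| 40/50/60% | 79% | 80% |
| 30/50/70% | 73% | 76% |
| 20/50/80% | 59% | 70% |
| 5/20/50% | 55% | 65% |

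**Step 5. Type I error of the pooled test.** With arms balanced within site, the last four rows give true levels of 4.4%, 3.6%, 2.2% and 2.9%, against 4.9 to 5.1% stratified. The reason can be seen for 20/50/80%. The within-site variance averages (0.16 + 0.25 + 0.16)/3 = 0.19, but the pooled test uses 0.5 × 0.5 = 0.25, so its z statistic has SD √(0.19/0.25) = 0.87 instead of 1. With simple randomisation ignoring site, the pooled test keeps a level of 4.8 to 5.1%.

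**Step 6. Group C.** Pooling C with D adds 12 RMPRU infants to each dose arm and 3 × 4 = 12 to placebo, so it does not itself unbalance arms by site.

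**The case against.** The strongest reply is that nothing here is wrong. An unadjusted comparison of randomised arms is valid, and by-site display is descriptive. A reader might infer from sections 5.4 and 5.7 that the SAP promised site-adjusted tests and then broke that promise. It did not. That part of the reply stands in full.

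Second, the large losses need implausible inputs. A gain of about 10 points requires placebo rates such as 20/50/80% at sites that share one protocol grading scale. Placebo seroresponse is expected to be below 20% (section 4), so such rates do not apply to the responder endpoints, where vaccine-placebo power (50% vs 20%, one-tailed) is already above 99.9%. This also stands, and it limits the claim to small gains on the planned contrasts.

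Third, the primary infant hypothesis, that at least 60% respond to two or more strains in some group, is read from per-arm proportions with Clopper-Pearson intervals, which a site term does not change. Phase 3 dose selection rests on an overall evaluation of the endpoints. Both are true, but section 7 still plans formal tests between groups, and those are what this point concerns.

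Fourth, a reader might infer that the unadjusted tests are conservative and their intervals too wide. That holds only if arms were balanced within site. This SAP does not say so, and the protocol is not at hand. The power loss does not depend on that condition.

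**Conclusion.** The point holds as a modest loss of efficiency. The pooled infant tests omit a recorded three-level factor. If sites differ, power is lost; if they do not, adding the factor costs essentially nothing (79.8% against 79.6% in the equal-rates case).

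The size is an assumption, because the SAP gives no between-site figures. It is about 0.1 to 1.2 points for the 2-fold GMT contrast with 0.6 as the total SD, about 0.5 to 3 points for 65% vs 80%, under 1 point for event rates with modest site spreads, and about 10 points only for extreme spreads.

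If arms were balanced within site, the unadjusted test is also conservative, at about 2 to 4.5% in the simulated cases with the wider spreads. If allocation ignored site, it keeps its 5% level and only power is lost. The documents do not support reading this as inflated type I error, as an error in the stated power, or as a serious weakening of the planned infant comparisons.

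**What to change.** In SAP section 7, for the pooled infant analyses (Groups C and D):
- Add site as a fixed effect with three levels, counting Group C infants as RMPRU, in the ANOVA, the logistic regressions and the mixed-effects reactogenicity model.
- For sparse events such as SAEs, use a site-stratified exact or Mantel-Haenszel test.
- Where Kruskal-Wallis or Wilcoxon applies, use a site-stratified rank test: van Elteren for pairs, and its multi-group counterpart for the overall test.
- Leave adults, toddlers and shedding as they are, since each comes from RMPRU only.

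Make the change before unblinding. The cost is a few lines of text and two degrees of freedom. Odds ratios become site-conditional, so the SAP should say so where they are reported. The per-arm proportions and their exact intervals do not change.

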3.3.1 Inclusion Criteria

Fulfillment of all of the following criteria is required to accept an adult, toddler or infant in the study:

1. Healthy adults, toddlers and infants as established by medical history and clinical examination before entering the study
2. Age:
Adults: ≥ 18 and ≤ 45 years old at time of enrollment
Toddlers: ≥ 2 and < 3 years old at the time of enrollment
Infants: ≥ 6 and < 8 weeks at the time of enrollment
3. Participant (adults) or parental (toddlers and infants) ability and willingness to provide written informed consent
4. Intention for the participant (and for toddlers and infants, the parent) to remain in the area with the child during the study period
5. If female and of childbearing potential, be not breastfeeding and not pregnant (based on a negative serum pregnancy test at screening and a negative urine pregnancy test at each study injection visit, prior to injection), planning to avoid pregnancy for at least 4 weeks after the last injection, and willing to use an adequate method of contraception consistently and have repeated pregnancy tests prior to second and third injections.

3.3.2 Exclusion Criteria

Any of the following will exclude an adult, toddler or infant from the study:

1. Presence of fever on the day of enrollment (axillary or oral temperature $>37.6^{\circ}\text{C}$)
2. Acute disease at the time of enrollment
3. Concurrent participation in another clinical trial throughout the entire timeframe for this study
4. Presence of malnutrition or any systemic disorder (cardiovascular, pulmonary, hepatic, renal, gastrointestinal, hematological, endocrine, immunological, dermatological, neurological, cancer or autoimmune disease) as determined by medical history and/or physical examination that would compromise the participant's health or is likely to result in nonconformance to the protocol
5. For infant cohort, history of premature birth (<37 weeks gestation)
6. History of congenital abdominal disorders, intussusception, or abdominal surgery
7. Known or suspected impairment of immunological function based on medical history and physical examination
8. For infant cohort only, prior receipt of rotavirus vaccine
9. A known sensitivity or allergy to any components of the study vaccine
10. History of anaphylactic reaction
11. Major congenital or genetic defect

12. Parents of participating toddlers or infants not able, available or willing to accept active weekly follow-up by the study staff
13. Receipt of any immunoglobulin therapy and/or blood products in the last 6 months or planned administration during the study period
14. History of chronic administration (defined as more than 14 days) of immunosuppressant medications, including corticosteroids, in the last 6 months (those on inhaled or topical steroids may be permitted to participate in the study)
15. Any medical condition in the participant (or parents of toddler and infant participants) that, in the judgment of the investigator, would interfere with or serve as a contraindication to protocol adherence or a participant's (or parents') ability to give informed consent
16. Clinically significant screening laboratory value*
17. HIV infection
 - a. For adults and toddlers, to be assessed by HIV ELISA
 - b. For infants, to be assessed by PCR, if mother is not known to be negative (negative test result between 24 weeks gestation and screening).

*Grade 1 laboratory abnormalities (see toxicity table in Appendix I) will not be considered to be exclusionary at screening unless judged to be clinically significant by the PI. Potential participants with laboratory values of grade 2 or higher are not to be randomized without concurrence of the Emmes medical monitor and PATH medical officer.

After informed consent has been obtained and the potential participant is identified as meeting inclusion and exclusion criteria for enrollment, the (s)he will be enrolled in the study and assigned a randomization number.

